Building upon this extensive clinical and regulatory foundation, Erchonia Corporation has developed the PPL Laser, which emits a low-powered blue wavelength. The PPL Laser is intended for use as a pre-treatment adjunct to the standard red laser therapy, with the goal of enhancing therapeutic outcomes in patients with nociceptive musculoskeletal pain.

This clinical study protocol is modeled closely after Erchonia's previous study that supported FDA market clearance for the red laser device (PL3000 cleared under K012580) indicated for "adjunctive use in providing temporary relief of minor chronic neck and shoulder pain of musculoskeletal origin." The key distinction in this protocol is the inclusion of a 5-minute pre-treatment protocol using the Erchonia PPL Laser—delivering low-level blue diode light to the neck and shoulder region—followed by a 13-minute application of the standard Erchonia red diode laser therapy.

For the red laser application, this study will utilize the Erchonia XLR8 device, which represents the current generation of Erchonia's red laser systems. The XLR8, cleared under K211186 for the same IFU of "*adjunctive use in providing temporary relief of minor chronic neck and shoulder pain of musculoskeletal origin*" has been determined to be substantially equivalent to its Erchonia predecessor models—including the PL3000, originally cleared under K012580.

DEVICE INFORMATION : ERCHONIA® PPL

DEVICE DESCRIPTION & DETAILS

The Erchonia® PPL is a non-thermal, non-invasive low-level laser device designed to be administered prior to administration of the standard Erchonia red laser therapy for the adjunctive temporary relief of nociceptive musculoskeletal pain. The handheld device utilizes two patented electronic semiconductor diodes emitting visible blue light at a wavelength of 450 nanometers, each with a power output of 8.75 mW.

The system is classified as a Class II laser under IEC 60825-1 and is compliant with 21 CFR 1040.10 and 1040.11, as modified by Laser Notice No. 50. Powered by an internal rechargeable battery, the PPL recharges via an inductive charging base using an external Class II medical-grade power supply compatible with 120V/60Hz and 220V/50Hz AC mains power. A built-in touchscreen interface serves as both a control panel and display, communicating directly with the internal printed circuit board (PCB) to initiate or pause laser emission.

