This pivotal study was a prospective, multi-center, randomized, double-blinded placebo controlled dual-arm study of 100 subjects, of which 86 passed screening and were available for primary endpoint analysis. Subjects were adults with neck and shoulder pain of musculoskeletal origin (osteoarthritis, chronic muscle spasms and cervical and thoracic spine sprain strain) ongoing for at least 30 days with a recorded 0-100 VAS pain scale rating of 50 or greater. Average duration of neck and/or shoulder pain at study entry was about 6 years. Red laser light therapy was administered to the sagittal suture (top of head); left and right cervical, shoulder and torso areas; right and left shoulders during each of passive external rotation and passive adduction of the arm and shoulder; right and left cervical muscles and trapezius muscles during passive left lateral flexion of the cervical spine; and the right and left sternocleidomastoid and scalene muscles during passive range of motion, for a total of 13 minutes during a single treatment administration. Post-treatment follow-up period was 48 hours.

Primary efficacy success was evaluated immediately following the single device treatment administration relative to baseline as the change in neck and shoulder pain rating as recorded on the 0-100 VAS. Individual subject success was defined as a 30% or greater improvement (decrease) in the primary efficacy measure from baseline to endpoint. Study success was defined as a minimum 30% difference between treatment groups, comparing the proportion of individual successes. 65.1% of actively treated subjects attained individual success compared with 11.6% of control (placebo) subjects, resulting in a 53.5% difference between treatment groups, exceeding the 30% criteria by 23.5% ($p < 0.0001$). Hence the study met its primary efficacy endpoint. Additionally, the magnitude of the mean change in neck and shoulder pain VAS rating at endpoint relative to baseline was -29.02 for actively treated subjects and -4.91 for control (placebo) subjects, a 20.08 difference ($p < 0.0005$). No treatment-related adverse event was reported or observed for any subject throughout study duration, and no other safety issues occurred.

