Study primary outcome measure was change in Visual Analog Scale (VAS) neck and shoulder pain rating from baseline to study endpoint evaluation. Individual subject success criteria was established as a 30% or greater decrease in VAS rating at endpoint relative to baseline. The study was pre-established as a non-inferiority study (equivalency or superiority) of the EVRL in red/violet diode combination therapy compared to the red diode only therapy as based upon the comparative data from the 2001 trial. Overall study success criteria was established as 65±5% of individual subject successes in the current trial. Seventy-five per cent (75%) of subjects in this dual diode violet/red laser study attained individual subject success compared with 65.1% of actively treated subjects in the 2001 trial, exceeding the overall study success criteria by 5%. The 29.80-point mean decrease (from 65.00 to 35.20) in neck and shoulder VAS pain rating from study Baseline to Endpoint for subjects in the violet/red laser study was comparable to (slightly above) the respective 29.02-point mean decrease (from 60.21 to 31.19) for the 2001 Active study subjects. As in the 2001 red laser only study, no adverse or other safety events were reported or recorded across study duration.

It was concluded that the application of simultaneous violet and red laser light was non-inferior to the application of red laser light alone in providing adjunctive temporary relief of minor chronic neck and shoulder pain of musculoskeletal origin.

3. The above two Erchonia-sponsored clinical trial outcomes, in addition to the below two Erchonia-sponsored clinical trial outcomes provided primary support for clearance of the indication for '*adjunctive use in providing temporary relief of nociceptive musculoskeletal pain*' for the respective light therapy devices:

➤ **CHRONIC LOW BACK PAIN:**

➤ **CHRONIC PLANTAR FASCIITIS HEEL PAIN:**

STUDY JUSTIFICATION

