The clinical study that supported clearance of K191257 and K212595 was a single arm (active treatment only), historical comparative design to demonstrate non-inferiority of the standard Erchonia red laser therapy when used in simultaneous combination with violet laser therapy compared with application of the standard Erchonia red laser therapy protocol alone in the temporary reduction of neck and shoulder pain of musculoskeletal origin. The historical comparative active data set for that clinical study used for non-inferiority analysis was the results from the Erchonia® red diode therapy only active subject group attained in the 2001 trial whose results successfully supported 510(k) clearance (K012580) of application of red laser light therapy only for the identical indication. This same historical comparative active data set will be used as the historical comparative Erchonia red laser therapy only active treatment data set for the current proposed clinical study.

SUBJECT GROUP

There will be a single subject group treated in this study. All subjects will receive the active study treatment with the blue laser therapy using the Erchonia® PPL first followed sequentially with the standard Erchonia red laser therapy (*Erchonia XLR8, FDA cleared under K211186*)

Comparative subject data for the red diode alone procedure administration will be taken from the Erchonia 2001 study whose results supported FDA market clearance for K012580.

BLINDING

As all subjects in this study will receive active treatment administrations with the Erchonia® PPL and the Erchonia XLR8, neither subjects nor investigators will be blinded. The statistician analyzing the study results will however be blinded with respect to study success analysis. The data from this combined laser therapy study and the retrospective comparative data from the 2001 red diode only study will be deidentified and presented to the study statistician as 'Group A' and 'Group B'. The statistician will not be aware of which group – A or B – contains the current combined laser therapy data and which contains the retrospective comparative red diode only data.

RANDOMIZATION

As this study is a single treatment group study, randomization to treatment group is not applicable. Therefore, this is a non-randomized trial.

SUBJECTS

Subject Sample

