The treatment administration protocol with the red laser device in this current study is identical to that which was evaluated in the comparative retrospective study to enable direct comparison of findings between the two studies and statistical analysis of different group outcomes. The only modification in the current study is the addition of a 5-minute treatment with the Erchonia PPL laser, administered immediately prior to the red laser therapy which is the treatment arm being evaluated for non-inferiority.

TREATMENT ADMINISTRATION PHASE EVALUATIONS: STUDY ENDPOINT

Within three (3) minutes of completion of the procedure administration phase, study endpoint evaluation will occur.

OUTCOME ASSESSMENTS

- Visual Analog Scale (VAS) Degree of Pain Rating
- Linear Range of Motion (ROM)
- Subject Satisfaction with Study Outcome Rating
- Adverse Events Evaluation

POST-TREATMENT ACTIVITIES

The post-treatment evaluation phase of this study will commence immediately following completion of the treatment administration phase evaluations and will last for two (2) days (48 hours).

The post-treatment outcome assessments will be recorded by the subject in his or her own home on forms provided by the test site. The subject will be instructed on when and how to complete the forms and how to return them to the test site prior to leaving the test site on the treatment administration day.

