The primary efficacy outcome measure for this clinical study is identical to that of the comparative reference study and is defined as the change in subject self-reported Visual Analog Scale (VAS) pain rating from baseline to study endpoint evaluation, with study endpoint defined as within 3 minutes of completion of the study single sequential treatment administration with the Erchonia® PPL blue laser therapy followed by the standard Erchonia red laser therapy administered using the Erchonia® XLR8.

Individual Subject Success Criteria

individual subject success criteria is defined as a 30% or greater decrease in self-reported neck and shoulder pain rating on the 0-100 VAS at study endpoint relative to baseline.

Overall Study Success Criteria.

Overall study success criteria is defined as at least 65%±5% of subjects in the current study meeting the study individual subject success criteria.

Justification for Study Success Criteria

The clinical relevance and justification of the individual and overall study success criteria is as follows:

- This study is a non-inferiority study, such that the research hypothesis is that the sequential combination therapy with the Erchonia® PPL blue laser and the standard Erchonia red laser therapy is either equivalent to or superior to the standard Erchonia red diode only therapy in effecting a clinically meaningful reduction in neck and shoulder pain of musculoskeletal origin, based upon the data attained from the red diode only clinical trial conducted in 2001 whose results successfully supported 510(k) clearance of application of the PL3000 red diode only for the identical indication being sought through the results of this clinical trial.
- The individual subject success criteria in this clinical study is identical to that of the comparative reference study.
- The overall study success criteria in this clinical study is based on the actual proportion of individual subject successes attained during the comparative reference trial for the active red diode treatment group, of 65%. The $\pm 5\%$ is the selected equivalence margin (δ), the maximally clinically acceptable difference for which the range of values (60% to 70%) for which the efficacies are “close enough” to be considered equivalent.
- Non-inferiority will be established if the proportion of subjects who attain the individual subject success criteria is no more than 5% less than the reference subject group (i.e. no less than 60%).

Hypotheses

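### The 65% reference rate comes from blinded subjects and the current subjects are unblinded; the comparability statement and the planned conclusion leave this difference out

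*Combined protocol and SAP*

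**What the plan says.** The justification for the treatment administration protocol states that the red-laser procedure matches the reference study so that findings can be compared directly between the two studies. It continues: "The only modification in the current study is the addition of a 5-minute treatment with the Erchonia PPL laser".

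Under Supporting Erchonia Corporation Clinical Data, the reference study is described as a "prospective, multi-center, randomized, double-blinded placebo controlled dual-arm study of 100 subjects". The result given is "65.1% of actively treated subjects attained individual success compared with 11.6% of control (placebo) subjects". The summary of the later red/violet study attributes the same active rate to the reference data: "compared with 65.1% of actively treated subjects in the 2001 trial".

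For the current trial, the Blinding section says that "neither subjects nor investigators will be blinded". Only the statistician is masked, by Group A and Group B labels. On the device, the Regulatory Background section says "For the red laser application, this study will utilize the Erchonia XLR8 device", and adds that this device was found substantially equivalent to its predecessors, including the PL3000.

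The primary endpoint is a fall of at least 30% in the subject's own VAS rating, taken within 3 minutes of the end of treatment. The decision rule reads: "Non-inferiority will be established if the proportion of subjects who attain the individual subject success criteria is no more than 5% less than the reference" group, that is, not below 60%.

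**The concern.** The 2001 subjects rated their pain knowing that they might have received placebo. Current subjects rate theirs knowing that they received an active laser, preceded by a second laser presented as an enhancement. They do so almost at once, at the clinic that treated them. Masking the statistician cannot change a mark already made.

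Any gain from that knowledge is counted for the blue-plus-red regimen. In a non-inferiority comparison this works against caution: it can hide a true loss of effect. It also means that a good result cannot be assigned to the blue laser, because masking and the added laser change together. The plan neither names the masking difference as a limitation nor allows for it, yet the SAP states its aim and hypotheses in terms of the treatment effect of the sequential regimen against red laser alone.

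**Working it through.** **Inputs from the documents.** Reference active arm: 43 subjects, 65.1% responders. Reference placebo arm: 11.6%; 86 subjects analysed in total. Current sample: 43. Margin: 5 points. Threshold: 60%.

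**Step 1: reproduce the reference figures.** With 43 per arm (86 − 43 = 43 on placebo), 28/43 = 65.1% and 5/43 = 11.6%. The difference is 53.5 points, as stated. The double-blind study and the 2001 data are the same source: both carry the 65.1% active rate and the 29.02-point mean fall.

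**Step 2: set the two studies side by side.**

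| Feature | 2001 reference arm | Current trial |
|---|---|---|
| Allocation | Randomised, active or placebo | Single arm |
| Subject and investigator masking | Double-blind | None |
| Red device | PL3000 | XLR8, stated to be substantially equivalent |
| Added treatment | None | 5 minutes of blue laser |
| Endpoint | Self-rated VAS just after treatment | Self-rated VAS within 3 minutes |

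The justification section mentions only the added treatment. The device change is covered elsewhere. Masking is described for each study separately but never named as a difference between them.

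**Step 3: express the margin in subjects.** 0.05 × 43 = 2.15. Since 25/43 = 58.1% fails and 26/43 = 60.5% passes, success needs 26 responders. The reference arm had 28.

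**Step 4: illustration with an assumed gain.** The documents give no unblinded rate for red laser alone, so both the blinded-equivalent rate of 55% and the gains below are assumptions. The chance of success is P(X ≥ 26), with X binomial (43, p) and p = 0.55 + gain.

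| Assumed gain | p | Chance of at least 26 of 43 |
|---|---|---|
| 0 points | 0.55 | 28.7% |
| 5 points | 0.60 | 54.1% |
| 10 points | 0.65 | 78.5% |

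**Step 5: separate the gain from the decision rule.** Much of the size in Step 4 comes from judging success on the observed proportion alone: 28.7% pass at a true 55% with no gain at all. If H0: P ≤ 60% were tested exactly at one-sided 0.05 (an assumed level, since none is stated for the proportion), success would need 32 of 43, with P(X ≥ 32) = 3.5% at p = 0.60. The same three scenarios then give 0.7%, 3.5% and 12.7%. The gain still raises the chance of a wrong conclusion, but from a much lower base.

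**Step 6: the nearest data in the documents.** The earlier red/violet study was also single-arm and active only. Its responder rate was 75% (33/44), which is 75 − 65.1 = 9.9 points above the reference. Its mean fall relative to baseline was 29.80/65.00 = 45.8%, against 29.02/60.21 = 48.2% in the 2001 active arm. One measure is higher and the other is not, and both are confounded with the violet laser. They do not measure expectation.

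**The case against.** A reader might infer that the plan flatly contradicts itself or conceals the changes. The documents do not support that. The sentence about the only modification stands in a section on treatment administration and follows a sentence about the red-laser procedure, so it can fairly be read as describing the procedure alone. The lack of blinding has its own section and a reason. The XLR8 is named, and its equivalence to the PL3000 is asserted.

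A reader might also infer that the plan does nothing to standardise the rating. It does: the VAS section fixes a scripted question, an unmarked line and a single mark, and tells the subject not to think of a number. Whether baseline and endpoint use separate forms depends on the case report forms in Appendix C, which were not available here.

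Finally, the single-arm historical design was chosen openly, as a replicate of one that the protocol describes as accepted by the FDA, and a single-arm trial cannot blind its subjects to treatment.

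These points narrow the concern but do not remove it. The sentence refers to the current study and is used to justify comparing findings across studies. Stating that current subjects are unblinded does not tell the reader that the comparator was blinded. Precedent does not remove the bias, and a script does not cover who is present or whether the earlier mark is visible.

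**Conclusion.** The concern holds as a point about comparability and interpretation. The reference rate was obtained under blinding and the current rate will not be. The endpoint is open to expectation, and the plan neither acknowledges the difference nor limits its conclusion.

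The direction, favouring the new regimen, is a reasonable inference from the design. The size is unknown. What can be said is that a 5-point gain would equal the whole margin, about 2 of 43 subjects, and a 10-point gain would be twice that (4.3 subjects).

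It would be tempting to read 28.7%, 54.1% and 78.5% as the effect of unblinding. They are not: they rest on an assumed true rate and assumed gains, and they largely reflect the point-estimate rule. Nor do the documents show that the regimen will be wrongly declared non-inferior. The device change is a minor part of the point because it is disclosed and addressed. Overall this is a worthwhile, inexpensive improvement, below the level of a required correction.

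**What to change.** 1. **Comparability statement.** In the justification for the treatment administration protocol, state that the comparison is between unblinded PPL plus XLR8 and the blinded PL3000 active arm of the 2001 trial, and that masking differs as well as the added laser.
2. **Conclusion.** In the SAP's primary outcome section, including the success criteria and hypotheses, limit the conclusion to the responder rate of the combined regimen relative to a historical blinded rate. Do not attribute a difference, or its absence, to the blue laser.
3. **Rating procedure.** Keep the existing VAS script. Add that the subject marks the baseline and endpoint scales on separate blank forms, out of the operator's sight and without seeing the earlier mark. Check Appendix C first, since it may already provide part of this.

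If the binomial scenarios are reported, label them as illustrations under assumed gains. A rule that calls any result within 2 responders of the threshold fragile is not advised: it would cover 28/43, the reference rate itself, and the 2 comes from the margin rather than from any estimate of bias.

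The cost is protocol wording and, if needed, a revised form and instruction sheet, with no extra subjects or staff. The price is a more cautious claim. Subjects remain unblinded, so these steps reduce the bias and describe it honestly but do not remove it.

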24 HOURS AND 48 HOURS POST-TREATMENT EVALUATIONS

The subject will be required to record the following at home on the forms provided by the test site at 24 hours and again at 48 hours after completion of the treatment administration phase at the test site.

OUTCOME ASSESSMENTS

- Visual Analog Scale (VAS) Degree of Pain Rating
- Linear Range of Motion (ROM)
- Subject Satisfaction with Study Outcome Rating
- Adverse Events Evaluation

STATISTICAL ANALYSIS PLAN

Populations Examined

Two (2) subject populations will be analyzed, as applicable:

- (i) **Intent-to-Treat (ITT) Population:** All enrolled subjects regardless of whether any measures are recorded and/or treatment is administered.
- (ii) **Per-Protocol (PP) Population:** All enrolled subjects who completed the study per protocol through to the 48-hour post-treatment evaluation, excluding subjects with major protocol deviations, incompletes, etc.

Primary analysis of efficacy will be according to the intent to treat (ITT) population and the secondary supportive analysis will be according to the per protocol (PP) population. Non-inferiority will be established if both the ITT and PP analyses agree.

Handling of Missing Data

Missing data will be handled through multiple imputation analysis, a strategy to handle missing values in a clinical trial wherein each missing value is replaced with a set of plausible values that represent the uncertainty about the right value to impute. The exact method of multiple imputation analysis will be determined after study completion depending on factors such as the amount of missing data and whether it is determined that the data are missing at random (MAR) or missing not at random (MNAR).

PRIMARY EFFICACY OUTCOME MEASURE: CHANGE IN SUBJECT SELF-REPORTED VAS PAIN RATING FROM BASELINE TO STUDY ENDPOINT

The aim of this study is to determine if the treatment effect of the sequential therapy with the Erchonia® PPL blue laser therapy followed by the Erchonia® XLR8 standard red laser therapy for the active treatment group in this study is equal to or superior to that attained for the active comparative treatment group in the comparative reference study who received the standard red laser therapy alone.

Proportion of Successes

The primary efficacy outcome measure for this clinical study is identical to that of the comparative reference study and is defined as the change in subject self-reported Visual Analog Scale (VAS) pain rating from baseline to study endpoint evaluation, with study endpoint defined as within 3 minutes of completion of the study single sequential treatment administration with the Erchonia® PPL blue laser therapy followed by the standard Erchonia red laser therapy administered using the Erchonia® XLR8.

Individual Subject Success Criteria

individual subject success criteria is defined as a 30% or greater decrease in self-reported neck and shoulder pain rating on the 0-100 VAS at study endpoint relative to baseline.

Overall Study Success Criteria.

Overall study success criteria is defined as at least 65%±5% of subjects in the current study meeting the study individual subject success criteria.

Justification for Study Success Criteria

The clinical relevance and justification of the individual and overall study success criteria is as follows:

- This study is a non-inferiority study, such that the research hypothesis is that the sequential combination therapy with the Erchonia® PPL blue laser and the standard Erchonia red laser therapy is either equivalent to or superior to the standard Erchonia red diode only therapy in effecting a clinically meaningful reduction in neck and shoulder pain of musculoskeletal origin, based upon the data attained from the red diode only clinical trial conducted in 2001 whose results successfully supported 510(k) clearance of application of the PL3000 red diode only for the identical indication being sought through the results of this clinical trial.
- The individual subject success criteria in this clinical study is identical to that of the comparative reference study.
- The overall study success criteria in this clinical study is based on the actual proportion of individual subject successes attained during the comparative reference trial for the active red diode treatment group, of 65%. The $\pm 5\%$ is the selected equivalence margin (δ), the maximally clinically acceptable difference for which the range of values (60% to 70%) for which the efficacies are “close enough” to be considered equivalent.
- Non-inferiority will be established if the proportion of subjects who attain the individual subject success criteria is no more than 5% less than the reference subject group (i.e. no less than 60%).

Hypotheses

- *Null Hypothesis:* Sequential treatment application of the Erchonia® PPL blue laser therapy followed by the standard Erchonia® red laser therapy using the XLR8 is inferior to treatment application of the Erchonia red laser therapy alone in reducing neck and shoulder nociceptive pain of musculoskeletal origin to the effect of 60% or fewer subjects attaining a 30% or greater reduction in neck and shoulder pain at study endpoint evaluation relative to baseline.

$H_0: P \leq 60\%$; where P = individual subject responder rate

- *Alternative Hypotheses:* Sequential treatment application of the Erchonia® PPL blue laser therapy followed by the standard Erchonia® red laser therapy using the XLR8 is NOT inferior to (i.e., is equivalent to or superior to) treatment application of the Erchonia red laser therapy only in reducing neck and shoulder nociceptive pain of musculoskeletal origin to the effect of greater than 60% of subjects attaining a 30% or greater reduction in neck and shoulder pain at study endpoint evaluation relative to baseline.

$H_1: P > 60\%$; where P = individual subject responder rate

Evaluation Time Point

Study endpoint evaluation was preestablished as occurring immediately (within 3 minutes) following completion of administration of the second component of the sequential study treatment with the standard Erchonia® red light laser device. Study primary success analysis is preestablished at study endpoint relative to baseline, identically to that in the 2001 reference comparative study.

Change Scores

- T-test analysis of the difference in the mean change in VAS levels from baseline to endpoint between the dual-diode and red only diode treatment administration groups. Significance levels will be considered at the $p < 0.05$ level.
- A t-test for two independent sample will be performed to evaluate the significance of the difference in the mean change in VAS pain scores from baseline to endpoint evaluation between the two study groups to evaluate for equivalency to support the support the conclusion of the proportion of successes evaluation. Significance levels will be considered at the $p < 0.05$ level.

SECONDARY EVALUATIONS

The following secondary evaluations will be performed on the per protocol study data set only. As no claims are intended to be made based on secondary measures, the findings will be presented through descriptive analysis and qualitative trending only, without evaluation for or claims of statistical significance.

- Change in mean neck and shoulder pain VAS ratings across study duration: baseline, endpoint, 24 hours, and 48 hours post-procedure.
- Change in linear ROM measurements at study endpoint relative to baseline.
- Subject satisfaction with study outcome ratings across study duration.

INDIVIDUAL TEST SITES

Results will be presented by individual test site for comparison.

INDIVIDUAL SUBJECT RESULTS

Individual subject results for the primary study outcome measure will also be presented.

SAFETY ANALYSIS

Safety analysis will be based on all enrolled subjects and will be assessed by evaluating and comparing the frequency and incidence of observed and/or reported adverse events between subjects enrolled in the current study and subjects enrolled in the comparative reference study. A chi-square test with a continuity correction will be performed to compare the percentage of subjects who had adverse events between the two subject groups.

ADVERSE EVENTS

At each evaluation and measurement point throughout the clinical study, and at any other time throughout the duration of the clinical trial that is necessary, all potential adverse events reported by a subject or observed by an investigator will be recorded on the case report form, and subsequently evaluated by the investigator for its relation to the study procedure and whether any corrective action needs to be taken. All potential adverse events recorded will be appropriately reported to the governing IRB, as applicable.

It is unlikely and not expected that any adverse events will result from implementation of this clinical study protocol. Prior clinical trials evaluating application of Erchonia low level laser light, including numerous evaluating Erchonia lasers for the treatment of various pain conditions, including neck and shoulder nociceptive pain of musculoskeletal origin, have not typically yielded any adverse events or reactions.

ADVERSE EVENTS DEFINITION

An adverse event means any untoward medical occurrence associated with the use of an intervention in humans, whether or not considered intervention-related (21 CFR 312.32 (a)).

SERIOUS ADVERSE EVENTS (SAE) DEFINITION

An adverse event (AE) or suspected adverse reaction is considered "serious" if, in the view of either the investigator or sponsor, it results in any of the following outcomes: death, a life-threatening adverse event, inpatient hospitalization or prolongation of existing hospitalization, a persistent or significant incapacity or substantial disruption of the ability to conduct normal life functions, or a congenital anomaly/birth defect. Important medical events that may not result in death, be life-threatening, or require hospitalization may be considered serious when, based upon appropriate medical judgment, they may jeopardize the subject and may require medical or surgical intervention to prevent one of the outcomes listed in this definition.

It is not anticipated that any SAE will occur from participation in this study.

UNANTICIPATED ADVERSE DEVICE EFFECT (UADE) DEFINITION

An unanticipated adverse device effect is defined as any serious adverse effect on health or safety, or any life-threatening problem or death caused by, or associated with, a device, if that effect, problem, or death was not previously identified in nature, severity, or degree of incidence in the investigational plan, or any other unanticipated serious problem associated with a device that relates to the rights, safety, or welfare of subjects."

CLASSIFICATION OF AN ADVERSE EVENT

A. Severity of Event

All AEs will be graded for severity by the study investigator according to the following grading system definitions.

- **Mild:** Event requires minimal or no treatment and does not interfere with the subject's daily activities.

- **Moderate:** Event result in a low level of inconvenience or concern with the therapeutic measures. Moderate events may cause some interference with functioning.
- **Severe:** Event interrupts a subject's usual daily activity and may require systemic drug therapy or other treatment. Severe events are usually potentially life-threatening or incapacitating.

B. Relationship to Study Intervention

All AEs will have their relationship to the study intervention assessed by the study investigator who examines and evaluates the subject based on temporal relationship and his/her professional clinical judgment. The degree of certainty about causality will be graded using the categories below. In a clinical trial, the study product must always be suspect.

- **Definitely Related:** There is clear evidence to suggest a causal relationship, and other possible contributing factors can be ruled out. The clinical event occurs in a plausible time relationship to study capsule administration and cannot be explained by concurrent disease, medications, or other treatments.
- **Probably Related:** There is evidence to suggest a causal relationship, and the influence of other factors is unlikely. The clinical event occurs within a reasonable time after administration of the study capsule, is unlikely to be attributed to concurrent disease, medications, or other treatments.
- **Not Related:** The AE is completely independent of study capsule administration, and/or evidence exists that the event is definitely related to another etiology. The alternative, definitive etiology must be fully documented by the clinician.

C. Expectedness

The study investigator will be responsible for determining whether an AE is expected or unexpected.

An AE will be considered **unexpected** if the nature, severity, or frequency of the event is not consistent with the risk information previously described for the study intervention.

An AE will be considered **expected** if the nature, severity, or frequency of the event is consistent with the risk information previously described for the study intervention.

TIME PERIOD AND FREQUENCY FOR EVENT ASSESSMENT AND FOLLOW-UP

The occurrence of an AE or serious adverse event (SAE) may come to the attention of study personnel during study visits and interviews of a study subject presenting for medical care, or upon review by a study monitor.

An **unsolicited AE** is defined as one that is reported without specific prompting or in response to a general question.

A **solicited AE** is one that is specifically solicited through asking a question regarding a specific potential AE.

Reporting and data collection for an AE will distinguish if a captured AE was unsolicited or solicited.

AEs will be collected throughout study duration.

REASONABLY ANTICIPATED AND POTENTIAL ADVERSE EVENTS

SAEs are not anticipated to occur in this clinical study.

There are no anticipated adverse events in this clinical study.

Potential adverse events that may feasibly occur from application of the Erchonia® PPL laser device include, but are not necessarily limited to skin irritation, discoloring, rash, indentations, or infection.

ADVERSE EVENT RECORDING

All AEs that occur, including local and systemic reactions, not meeting the criteria for SAEs will be captured on the appropriate AE case report form (CRF). Information to be collected includes event description, time of onset, clinician's assessment of severity, relationship to study product (assessed only by those with the training and authority to make a diagnosis), corrective action taken, time of resolution/stabilization of the event and if the subject was withdrawn from the study because of the AE. Recording will be done in a concise manner using standard, acceptable medical terms.

All AEs occurring while on study must be documented appropriately regardless of relationship. All AEs will be followed to adequate resolution.

Any medical condition that is present at the time that the subject is screened will be considered as baseline and not reported as an AE. However, if the study subject's condition deteriorates at any time during the study, it will be recorded as an AE.

Changes in the severity of an AE will be documented to allow an assessment of the duration of the event at each level of severity to be performed. AEs characterized as intermittent require documentation of onset and duration of each episode.

The study investigator will record all reportable events with start dates occurring any time after informed consent is obtained until 7 (for non-serious AEs) or 30 days (for SAEs) after the last day of study participation.

Events will be followed for outcome information until resolution or stabilization.

ADVERSE EVENT REPORTING

Adverse Event Reporting Timeframes

The table below lists the minimum AE reporting requirements for study Investigators. Reporting of all safety events to the Sponsor will be completed through Investigator submission of the AE CRF and any applicable supporting documentation

Table 1: Investigator AE Reporting Requirements

Type of AE	Report to	Reporting Timeframe (from time of learning of event)
Adverse Event (AE)	IRB	Per IRB reporting requirements
	Sponsor	Within 10 working days
Serious Adverse Event (SAE)	Sponsor	Within 24 hours
	IRB	Per IRB reporting requirements
Device Deficiency	Sponsor	Within 48 hours
	IRB	If SAE occurs due to the device deficiency, within 24 hours of learning of the event and per IRB reporting requirements
Device Related AE/SAE	Sponsor	Within 24 hours

Unanticipated Adverse Device Effect (UADE) Reporting

